### **10.3 Reporting**

Each AE is to be classified by the investigator as SERIOUS or NONSERIOUS based on the criteria in Section 10.1.2, SAEs.

All AEs that occur in study subjects during the AE reporting period specified in this protocol will be reported, whether or not the event is considered related to study drug (vadadustat or epoetin alfa).

#### **10.3.1 Reporting Period**

The AE reporting period for this study begins from time of randomization and ends at the final protocol-required Safety Follow-Up (Visit 15).

In addition, any SAE that occurs subsequent to the AE reporting period that the investigator assesses as related to the study drug will also be reported as an SAE.

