### 7.3 Exclusion Criteria

Subjects must not meet any of the following exclusion criteria:

1. Anemia due to a cause other than CKD (e.g., sickle cell disease, myelodysplastic syndromes, bone marrow fibrosis, hematologic malignancy, myeloma, hemolytic anemia, thalassemia, or pure red cell aplasia)
2. Active bleeding or recent blood loss within 8 weeks prior to randomization
3. RBC transfusion within 8 weeks prior to randomization
4. Anticipated to discontinue hemodialysis during the study
5. Judged by the investigator that the subject is likely to need rescue therapy (ESA administration or RBC transfusion) immediately after enrollment in the study

6. History of chronic liver disease (e.g., chronic infectious hepatitis, chronic autoimmune liver disease, cirrhosis or fibrosis of the liver)
7. Aspartate aminotransferase (AST)/serum glutamic oxaloacetic transaminase (SGOT), alanine aminotransferase (ALT)/serum glutamic pyruvic transaminase (SGPT), or total bilirubin >1.5 x upper limit of normal (ULN) during Screening. Subjects with a history of Gilbert's syndrome are not excluded.
8. Current uncontrolled hypertension as determined by the investigator that would contraindicate the use of epoetin alfa
9. Acute coronary syndrome (hospitalization for unstable angina or myocardial infarction), surgical or percutaneous intervention for coronary, cerebrovascular or peripheral artery disease (aortic or lower extremity), surgical or percutaneous valvular replacement or repair, sustained ventricular tachycardia, hospitalization for heart failure (HF) or New York Heart Association Class IV HF, or stroke within 12 weeks prior to or during Screening
10. History of new or recurrent malignancy within 2 years prior to and during Screening or currently receiving treatment or suppressive therapy for cancer. Subjects with treated basal cell carcinoma of skin, curatively resected squamous cell carcinoma of skin, or cervical carcinoma in situ are not excluded.
11. History of deep vein thrombosis or pulmonary embolism within 12 weeks prior to or during Screening
12. History of hemosiderosis or hemochromatosis
13. History of prior organ transplantation (subjects with a history of failed kidney transplant or corneal transplants are not excluded)
14. Scheduled organ transplant from a living donor and subjects on the kidney transplant wait-list who are expected to receive a transplant within 6 months

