### 9.3.1 Screening Visits

Subjects will need to sign a full consent form prior to SV1 procedures. The consent form may be signed in advance of the SV1 procedures. The Screening Period starts at the time the informed consent is signed and will be a maximum of 28-days in duration. Two Screening visits (SV1 and SV2, with a minimum of 4 days in between) must be performed within the Screening Period and prior to dosing (Baseline/Day 1).

A subject may enter the washout period only after all eligibility criteria have been met following SV2. During the washout period, no epoetin alfa will be administered before Baseline/Day 1 for 5 days in the Main study and 2 days in the ESA hyporesponder parallel study.

After obtaining informed consent, subjects will undergo a number of Screening activities.

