### **9.3.2 Baseline/Day 1 (Visit 1)**

Epoetin alfa dosing will have been stopped for a minimum of 5 days in the Main study or 2 days in the ESA hyporesponder parallel study until Baseline/Day 1.

On Baseline/Day 1, blood sample collection and other Baseline/Day 1 procedures will be completed prior to dosing with study drug (vadadustat or epoetin alfa). On Baseline/Day 1, study drug will be administered at the study site, and will be administered after the PK sample is collected and prior to the dialysis session.

At Baseline/Day 1, the following activities/procedures will be performed:

- Review of study eligibility criteria
- Review of acceptable methods of contraception
- Review of medical history for new conditions since SV2
- Review of medication use since SV2
- Randomization
- Introduction to and instruction on the use of the eDiary and paper dosing reminders
- SF-36v2, PGI-S, and EQ-5D-5L assessments
- Abbreviated, symptom-directed physical examination, at the discretion of the investigator, as clinically indicated
- 12-lead ECG: ECGs will be completed prior to blood draws when possible and will be obtained after the subject has been resting supine comfortably for approximately 5 minutes; ECG may be completed and reviewed by the investigator on Baseline/Day 1 or if needed for scheduling reasons (e.g., dialysis treatment is scheduled for early morning of Baseline/Day 1), the ECG can be completed and reviewed up to 1-3 days prior to Baseline/Day 1.
- Vital signs including temperature, HR, BP, and RR (assessed in seated position after 5 minutes of rest and prior to blood draws), and dry weight

- Laboratory Procedures:
  - CBC (including differential)
  - Reticulocyte count
  - CRP
  - Serum chemistry
  - LFTs
  - Iron indices
  - Lipid profile
  - Biomarkers (VEGF, and Hepcidin)
  - PK prior to vadadustat or epoetin alfa dosing (see [Section 9.2.2.1](#), PK/PD Sampling for Subjects Randomized to Vadadustat and [Section 9.2.2.2](#), PK Sampling for Subjects Randomized to Epoetin Alfa) and prior to the dialysis session
- Study drug assessments and procedures:
  - Subject will take/receive their first dose of study drug at the study site during Baseline/Day 1
  - For subjects in the vadadustat treatment arm only:
    - Initiate vadadustat dosing
    - Vadadustat drug dispensation
    - Review vadadustat dosing instructions
  - Epoetin alfa dosing will continue for the subjects in the epoetin alfa arm

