## 10 ADVERSE EVENTS

### 10.1 Definitions

#### 10.1.1 AEs

For the purposes of this study, an AE is any untoward medical occurrence (including an abnormal laboratory finding) that occurs in the protocol-specified AE reporting period; the event does not necessarily have a causal relationship with that treatment or usage.

An AE includes medical conditions, signs, and symptoms not previously observed in the subject that emerge during the protocol-specified AE reporting period, including signs or symptoms associated with pre-existing underlying conditions that were not present prior to the AE reporting period.

AEs therefore include the following:

- All AEs, whether suspected to be causally related to study drug or otherwise.
- All AEs secondary to any medication overdose, medication error, abuse, withdrawal, sensitivity, or toxicity.
- Illnesses apparently unrelated to study drug, including the worsening of a pre-existing illness (see paragraph below on Pre-existing Conditions).
- Injury or accidents. Note that if a medical condition is known to have caused the injury or accident (e.g., a fall secondary to dizziness), the medical condition (dizziness) and the accident (fall) will be reported as 2 separate AEs.
- Abnormalities in physiological testing or physical examination findings that require clinical intervention or further investigation (beyond ordering a repeat [confirmatory] test).
- Laboratory abnormalities that require clinical intervention or further investigation (beyond ordering a repeat [confirmatory] test) unless they are associated with an already reported clinical event. Laboratory abnormalities associated with a clinical event reported as an AE (e.g., elevated liver enzymes in a subject with jaundice) will be described under 'Comments' on the report of the clinical event rather than reported as separate AEs.

The following guidelines are to be used when reporting AEs for this study:

**Medical Diagnoses** – Whenever possible, a medical diagnosis term will be used to report AEs instead of signs and symptoms due to a common etiology, as determined by qualified medical study staff. For example, pneumonia will be the reported AE term, instead of fever and dyspnea, when the diagnosis has been established. Signs and symptoms will be reported as event terms only when the medical diagnosis remains unknown, and revised to a medical diagnosis term once it has been established.

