## 12 DATA HANDLING AND RECORD KEEPING

### 12.1 CRFs/EDC

This study will utilize an EDC system to manage data collection during this trial. The system is fully Code of Federal Regulations 21 part 11 compliant. An EDC system contains certain functionality including, but not limited to, a graphical user interface to help facilitate data entry, a data validation element to check user data, and a reporting function. CRFs available through this system are required and will be completed for each randomized subject.

Any form of data from the electronic system are the sole property of the sponsor and will not be made available in any form to third parties, except for authorized representatives of the sponsor or appropriate regulatory authorities, without written permission from the sponsor.

The investigator has ultimate responsibility for the accuracy, authenticity, and timely collection and reporting of all clinical, safety, and laboratory data entered in the EDC or any other data collection forms. The CRFs will be signed electronically by the investigator to attest that the data contained on the CRFs is true.

In most cases, the source documents are contained in the subject's chart at the hospital or the physician's office. In these cases, data collected on the CRFs will match the data in those charts.

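### Serious events during the required epoetin washout fall outside AE and SAE reporting, which starts only at randomization

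*Protocol*

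**What the plan says.** Section 10.3.1 sets the window: "The AE reporting period for this study begins from time of randomization and ends at the final protocol-required Safety Follow-Up (Visit 15"). Section 9.2.1 and Appendix A note [m] repeat the same start. Section 10.1.1 builds the window into the definition itself: "an AE is any untoward medical occurrence (including an abnormal laboratory finding) that occurs in the protocol-specified AE reporting period".

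Section 9.3.1 places the washout after SV2: "A subject may enter the washout period only after all eligibility criteria have been met following SV2". It adds that "no epoetin alfa will be administered before Baseline/Day 1 for 5 days in the Main study and 2 days" in the hyporesponder study. Section 9.3.2 describes the washout as already complete at the next visit: "Epoetin alfa dosing will have been stopped for a minimum of 5 days in the Main study" (2 days in the hyporesponder study). Randomization is on the list that follows the words "At Baseline/Day 1, the following activities/procedures will be performed".

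On records, Section 12.1 says: "CRFs available through this system are required and will be completed for each randomized subject". Section 9.1.3 asks sites to log the reasons why a screened subject was found ineligible.

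**The concern.** The washout is more than a waiting time in screening. Consented subjects stop a maintenance drug because the protocol requires it. The protocol recognises this kind of harm in principle: Section 10.1.1 counts events secondary to withdrawal of a medication among AEs, and the list of possible causes in Section 10.3.4 includes protocol-related procedures. Yet the one withdrawal imposed on every subject sits outside the window in which an event can be called an AE.

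Two things are at stake. A serious event in washout has no expedited route to the sponsor. The loss is also selective: several of the gravest events are exclusion criteria, so a subject who has one leaves before randomization. The safety of converting from epoetin, the setting named in the study title, is then described only in subjects who were still eligible at the end of the washout.

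**Working it through.** The protocol gives no washout event rate and no power calculation, so there is no stated figure to reproduce. The check compares the timing rules, then gives a scale.

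**Order of events**

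1. Washout begins only after eligibility is met following SV2 (Section 9.3.1).
2. Epoetin has been stopped for at least 5 or 2 days by Baseline/Day 1 (Section 9.3.2).
3. Randomization is a Baseline/Day 1 procedure (Section 9.3.2 and Appendix A).
4. AE reporting starts at randomization (Section 10.3.1).

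The whole required washout thus precedes reporting. Because an AE is defined by the window (Section 10.1.1) and an SAE is an AE that meets a seriousness criterion (Section 10.1.2), an event in washout is neither. Section 10.3.1 extends SAE reporting beyond the window only forward, for related events after Visit 15. Section 10.2 requires questioning about AEs only at visits after randomization.

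**What record remains**

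- *Subject later randomized.* Baseline/Day 1 includes a review of new medical conditions and medication since SV2 and of rescue therapy. The event becomes history, and under Section 10.1.1 a pre-existing condition is an AE only if it worsens or recurs more often.
- *Subject not randomized.* Eligibility is reviewed again at Baseline/Day 1 (Appendix A note [d]). Criterion 3 of Section 7.3 excludes "RBC transfusion within 8 weeks prior to randomization". Criteria 9 and 11 exclude acute coronary syndrome, stroke, DVT and PE during Screening, which contains the washout. CRFs are required only for randomized subjects (Section 12.1), so the required record is the logged reason (Section 9.1.3). The sentence on deaths in Section 10.3.3 is not limited to the window.
- *Analysis.* The Safety Population requires randomization and at least one dose (Section 11.2).

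**Scale of the uncovered time** (subjects x required days; enrollment from Section 11.1)

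| | Main | Hyporesponder | Total subject-days |
|---|---|---|---|
| Planned | 95 x 5 = 475 | 30 x 2 = 60 | 535 |
| Maximum expansion | 115 x 5 = 575 | 60 x 2 = 120 | 695 |

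These totals cover randomized subjects only. Subjects who start washout and are not randomized come on top, in a number that the protocol does not give.

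**Chance of at least one such event.** The rate p below is an assumption, with a range because the protocol gives none. The formula is 1 - (1 - p)^125, and the expected number is 125 x p.

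| Assumed share with a serious event in washout | Expected events in 125 | Chance of at least one |
|---|---|---|
| 0.2% | 0.25 | 22% |
| 0.5% | 0.62 | 47% |
| 1% | 1.25 | 72% |
| 2% | 2.5 | 92% |

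**The case against.** The strongest reply is that the start point is deliberate and consistent across Sections 9.2.1, 10.2 and 10.3.1 and Appendix A note [m], and that the washout precedes randomization in both arms, so it does not bias the comparison between them. That stands. The point concerns safety oversight, not the treatment contrast. The only reason recorded in the amendment history is a possible delay between randomization and first dose, which does not bear on washout.

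Four stronger readings are tempting, and the documents do not support them.

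- *That subjects are unobserved in washout.* They attend dialysis three times weekly. Those who reach Day 1 have conditions, medications, rescue therapy, laboratory tests, vital signs and ECG reviewed, and at least 8 weeks of ESA history is recorded. The 535 subject-days measure time outside AE/SAE reporting, not time without any record.
- *That an affected subject becomes a screen failure.* Section 9.3.1.2 states that rule only for non-qualifying Hb. Other events lead there only if they breach a criterion or the subject is otherwise not randomized. Resuming an ESA is not itself a listed exclusion.
- *That a subject could be off epoetin for about 24 days.* The subtraction 28 - 4 needs consent and SV1 on the same day, SV2 exactly 4 days later, washout starting at SV2 and Day 1 at the limit. Section 9.3.1 allows washout only once eligibility is met, which depends on SV2 results. Sections 8.4.1 and 9.3.1 also give the washout as 5 or 2 days without calling it a minimum, whereas Sections 6.1.1, 9.3.1.2 and 9.3.2 do call it one. Those statements should be reconciled.
- *That the pause causes coronary events, stroke or thrombosis.* Nothing in the protocol links a 2- or 5-day pause to them. Its background section ties cardiovascular risk to ESAs and higher Hb targets.

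It is also fair to say that a 2-day stop may fit within the usual gap between dialysis sessions, so the 60 hyporesponder days may involve no omitted dose. The 475 Main study days are the firmer part.

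**Conclusion.** The gap is real but narrower than a first look at the start date suggests. A serious event during the required washout is not reportable as an SAE and does not enter the safety analysis. This follows from the protocol's own definitions and needs no assumption about event rates. The uncovered time is at least 535 subject-days at planned enrollment and at least 695 at the maximum.

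The gap matters most for subjects who start washout and are never randomized, because a logged reason is then the only required record unless the subject dies. Their number is unknown and probably small. Whether any serious event would fall in this period depends on the assumed rate: 22% to 92% for rates of 0.2% to 2%. Those percentages cover events from any cause and say nothing about whether the washout produced them.

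Moving the start date would not by itself capture the most direct consequence of stopping epoetin. Section 10.1.1 does not treat worsening of anemia due to CKD as an AE in any period.

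**What to change.** - In Section 10.3.1, Section 9.2.1 and Appendix A note [m], start collection of SAEs, and of AEs attributed to stopping epoetin, on the first day of washout. Align Section 10.2 and the AE definition in Section 10.1.1 with that start.
- For any subject who starts washout and is not randomized, complete an SAE page and a page for transfusion and ESA use, and widen the CRF requirement in Section 12.1 accordingly. The second page is needed because CKD-related worsening of anemia would otherwise remain uncaptured.
- List these events separately from treatment-emergent AEs, and state how many subjects started washout and how many of them were not randomized.

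The cost is a few sentences, a short CRF page and a small number of extra pre-treatment reports. Sample size, treatment and the efficacy analysis do not change.

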#### **10.3.2 Reporting AEs**

NONSERIOUS AEs are to be reported on the AE CRFs.

#### **10.3.3 Reporting SAEs**

Any SAE, regardless of causal relationship, will be reported to the sponsor's Medical Monitor or CRO designee within 24 hours after the investigator becomes aware of the SAE. Compliance with this time requirement is essential so that the sponsor may comply with its regulatory obligations.

The initial SAE report should be completed as fully as possible but will contain, at a minimum items number 1 to 6:

1. Subject number/ID, sex, and age/date of birth
2. The date of report
3. Name of the reporter
4. Name of the suspected medicinal product

5. A description of the event, including event term(s), seriousness criteria, and a clinical summary of the event
6. Causality assessment

If the causality assessment is not provided in the initial report an updated report with the causality must be provided within 24 hours, once assessed.

Information about all SAEs (either initial or follow-up information) will be collected and recorded in English on the electronic SAE Report Form within the EDC system. The investigator will assess the relationship to each specific component of the study treatment. If the event meets serious criteria and it is not possible to access the EDC system, a paper SAE Report Form will be sent to the CRO via email or fax, or the investigator will call the CRO SAE hotline within 24 hours of being made aware of the SAE (reference the site manual for contact information). When the EDC system becomes available again, the SAE information will be entered within 24 hours of the system becoming available.

The investigator will report follow-up information relating to an SAE to the sponsor's Medical Monitor or CRO designee within 24 hours of awareness updating the electronic CRF with the new information or by submitting a paper SAE Report Form in the event that the EDC is not available. When the EDC system becomes available, the SAE information will be entered within 24 hours. The subject will be observed and monitored carefully until the condition resolves or stabilizes.

All deaths are to be thoroughly investigated and reported. Autopsy reports and death certificates are to be obtained, if possible.

The sponsor and/or its designee are responsible for reporting SAEs to all applicable regulatory agencies and the central ethics committees within the required timeline.

The investigators are responsible for submitting required safety information to their local IRB as per local regulations. This information includes, but is not limited to, any safety alert letter received from the sponsor and any SAEs occurring at their study site.

#### **10.3.4 Relationship to Study Drug**

The causal relationship of the AE to study drug (vadadustat or epoetin alfa) will be assessed by both the investigator and the sponsor.

The assessment of causal relationship to study drug will be evidence-based, and not based on the premise that all AEs are possibly causally related to study drug until proven otherwise.

Examples of evidence that would suggest a causal relationship between the study drug and the AE include the occurrence of an AE that is uncommon and known to be strongly associated with drug exposure (e.g., angioedema, hepatic injury, and Stevens-Johnson syndrome) or an AE that is uncommon in the population exposed to the drug.

The causal relationship of the AE is assessed using a binary system, and AEs are classified as either 'related' or 'unrelated';

Related: There is 'reasonable possibility' that the drug caused the AE. The AE follows a reasonable temporal sequence from the time of drug administration. There is supportive evidence (facts) to suggest a possible causal relationship, irrespective of the degree of certainty between the observed AE and the drug.

**Unrelated:** An AE does not follow a reasonable temporal sequence from administration of the product and/or there is no reasonable possibility that the drug caused the AE. This assessment includes situations where the AE is related to other factors such as the subject's clinical state, other therapeutic interventions, or concomitant drugs administered to the subject.

Default assessments using the 'related' category without supportive evidence for a causal relationship to study drug are generally uninformative and do not contribute meaningfully to the development of the safety profile of the drug or to subject protection.

Investigators are encouraged to choose the most plausible cause for the event(s) from the following list: medical history, lack of efficacy/worsening of treated condition, study treatment, other treatment (concomitant, or previous), withdrawal of study treatment, administration error, protocol-related procedure, others (specify).

